## 3.0 RESEARCH SUBJECT SELECTION

### 3.1 Eligibility Criteria

Eligible patients include women >20 years of age who plan to receive chemotherapy at DFCI to treat recurrent, incurable gynecologic cancers (i.e., ovarian, uterine, and cervical that has recurred despite  $\geq 1$  prior treatments), own a smart-phone (Android or iOS), are capable of downloading and running the study app, can read and provide informed consent in English, and do not have cognitive or visual impairments that would preclude use of the app.

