#### *Cancer experience question analysis plan*

We plan to analyze qualitative data from the cancer experience question using the Linguistic Inquiry and Word Count (LIWC) program, developed by James Pennebaker and colleagues and used widely in emotional expression literature with cancer patients and other populations. LIWC reads text and identifies which words are associated with psychologically-relevant categories, i.e. affect, cognitive processes, content dimensions, etc. Because the holistic nature of the responses may not be adequately captured by the word count approach of LIWC analyses, we also plan to perform a content analysis of the output from the cancer experience question with trained independent raters, examining categories of psychologically relevant content in the recordings. For Phase I, due to the limited sample size, analyses will be descriptive in nature. For Phase II, we plan to use multivariate analyses of covariance (MANCOVA) as primary statistical procedures, controlling for baseline values, on conceptually related groups of variables including physical health-related outcomes (i.e., symptoms and healthcare utilization), psychological adjustment as measured by other study instruments (i.e., quality of life and emotional acceptance), and psychological properties of participants' responses to the cancer experience question (i.e. positive and negative affect). We also plan to conduct preliminary multivariate analyses of variance for continuous variables and chi-squared analyses for categorical variables, on demographic variables, cancer-related parameters, and other relevant variables (e.g. quality of life) at baseline. If relevant, we will use the baseline values on these measures as covariates to control for nonsignificant chance variation between groups at baseline.

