#### Primary Endpoint: Second Phase

- 1) Health-related quality of life, comparing the patient-reported baseline and 6-month EuroQol EQ-5D.

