### 6.2 Sample Size and Statistical Power or Precisions

A convenience sample of 10 patients will be enrolled to the first phase of the study. Due to the limited sample size, statistical analysis will be descriptive in nature.

100 patients will be enrolled to the second phase of this study, which will employ a 2x2 factorial design as depicted in the table below. Patients will be randomized 1:1:1:1 to one of the four arms.

Fitbit	App	Arm	Sample size
+	Active	1 (Fitbit + active app)	25
+	Passive	2 (Fitbit + passive app)	25
-	Active	3 (Active app)	25
-	Passive	4 (Passive app)	25
		Total	100

For the outcome of change in EQ-5D, we will use a one-sided type I error rate of 5% to conclude that an intervention is promising for further study. Based on prior literature, the standard deviation of the change in EQ-5D at 6 months compared to baseline is approximately 14 points. With a total sample size of 100 patients (25 patients per arm), the table below summarizes the power to conclude that the either or both of the interventions are promising for further study based on a variety of effect sizes.

Difference in EQ-5D versus Usual Care			Power to conclude that intervention is promising for further study	
HOPE App	Wearable accelerometer	HOPE App + Wearable accelerometer	HOPE App	Wearable accelerometer
6	0	6	70%	--
7	0	7	80%	--
6	3	9	70%	28%
7	3	10	80%	28%
6	3	8	62%	23%
7	3	8	68%	17%

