For the primary analysis, the EQ-5D index scores will be calculated in each study arm at both baseline and 6 months and compared. The effect of the Fitbit on EQ-5D will be obtained by comparing the mean change in EQ-5D among all arms that consist of the Fitbit (i.e. arms 1 and 2) versus that obtained among all arms that do not consist of the Fitbit (i.e. arms 3 and 4). Similarly, the effect of the HOPE app on EQ-5D will be obtained by comparing the mean change in EQ-5D among all arms that consist of the HOPE app (i.e. arms 1 and 3) versus that obtained among all arms that do not consist of the HOPE app (i.e. arms 2 and 4). Additionally, pair-wise comparisons will be conducted of arms 2, 3, and 4 to arm 1 to examine which arms are driving or diluting any differences observed. Mean score changes from baseline will be compared using t tests and multivariable linear regression. The multivariable linear regression model will consist of change score as the dependent variable, and will adjust for baseline covariates (age, sex, cancer type, race, education, and literacy and numeracy). Additional analyses will use Fisher's exact test to compare the proportion of patients in each study arm who experience an improvement, no change, or a decrement in quality of life. This will be conducted both for any level of change from baseline and for a 6-point change from baseline (the threshold for a clinically meaningful difference). Similar analyses will be conducted for the secondary outcomes, including anxiety, depression, and number of patient phone calls, using the appropriate regression model (e.g. negative binomial regression may be used for the outcome of the number of patient phone calls).

For the health care utilization endpoints of unplanned infusion appointments, emergency room visits, and hospitalizations, cumulative incidence functions will be calculated with death treated as a competing event. Competing risk regressions will be used to model risk with and without adjustment for baseline covariates.

Agreement between patient-oncologist estimates of performance status will be estimated by Cohen's Kappa statistic, and differences in agreement between the study groups will be tested by bootstrapping.

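### The Phase 2 regression of EQ-5D change leaves out baseline EQ-5D, so it may lose precision and over-correct chance baseline imbalance

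*Combined protocol and SAP*

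**What the plan says.** The Phase 2 primary endpoint (section 6.1) is "Health-related quality of life, comparing the patient-reported baseline and 6-month EuroQol EQ-5D". Section 6.4 estimates each factor's effect as a difference in mean change: arms 1 and 2 against 3 and 4 for the Fitbit, and arms 1 and 3 against 2 and 4 for the app. It adds that "pair-wise comparisons will be conducted of arms 2, 3, and 4 to arm 1". The methods are t tests and a multivariable linear regression with "change score as the dependent variable, and will adjust for baseline covariates (age, sex, cancer type, race, education, and literacy and numeracy". The list has no open-ended qualifier, and section 6.5 on missing data does not extend it. The plan does not say whether the t test or the regression decides.

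Baseline EQ-5D-5L is in the Phase 2 baseline interview (Table 1), which all four arms complete at Visit 0 (Table 3). Randomization uses blocks of 8, and no stratification on baseline EQ-5D is described.

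The one place where baseline values are controlled is the analysis plan for the cancer experience question (section 5.21n): "we plan to use multivariate analyses of covariance (MANCOVA) as primary statistical procedures, controlling for baseline values". That is a different analysis.

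Section 3.1 reads "Eligible patients include women >20 years of age", so sex, which is on the covariate list, does not vary.

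**The concern.** A change score fixes the coefficient of the baseline value at 1. If the slope of 6-month on baseline EQ-5D is below 1, two things follow.

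- **Precision.** Part of the variance of change is explained by baseline. The planned model leaves it in the error term.
- **Chance imbalance.** In the one sample realized, any baseline difference between groups is subtracted in full when only part of it should be. This favours the group that happened to start lower. The effect is largest in the 25 v 25 comparisons with arm 1, which are meant to show which arms drive a result.

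The trial has about 69% power at its own 6-point threshold for a meaningful change, so precision that costs nothing to collect is worth having. The presence of sex in the list is a harmless drafting slip, since a constant drops out of the fit.

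**Working it through.** **Inputs from the documents.** SD of change: "the standard deviation of the change in EQ-5D at 6 months compared to baseline is approximately 14 points" (section 6.2). Test: "we will use a one-sided type I error rate of 5% to conclude that an intervention is promising for further study" (section 6.2). There are 25 patients per arm, so each factor compares 50 with 50.

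**Inputs that are assumptions.** The documents do not give the baseline to 6-month correlation r, or the ratio k of the 6-month SD to the baseline SD. Ranges are shown.

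**1. The plan's own figure.** SE = 14 × √(2/50) = 2.8. For 6 points, the noncentral t with 98 df gives 68.6% (normal approximation 69.1%), against 70% stated. For 7 points it gives 79.9%, against 80%. The stated power is therefore that of an unadjusted 50 v 50 change-score comparison, and it reproduces.

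**2. Adding baseline EQ-5D.** Let s be the baseline SD and ks the 6-month SD.

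- Fix s²(1 + k² − 2rk) = 14².
- The residual SD with baseline in the model is ks√(1 − r²).
- With k = 1 this reduces to 14√((1 + r)/2). At r = 0.5 it is 14 × √0.75 = 12.12.
- The df are 96 (intercept, Fitbit, app, baseline).

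Power for 6 points, against 68.6% unadjusted (a dash means not listed):

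| k | r = 0.3 | r = 0.5 | r = 0.7 | r = 0.8 | r = 0.9 |
|---|---|---|---|---|---|
| 1 | 84.0% | 79.2% | 74.6% | 72.5% | 70.5% |
| 1.1 | – | 76.1% | 71.6% | 69.8% | – |
| 1.25 | – | 72.8% | 69.3% | 68.5% | – |

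Baseline is uncorrelated with change when r = 1/k, so the gain is nil at k = 1.25, r = 0.8. Simulation with 8,000 trials per case agrees: 83.7%, 79.4%, 74.4% and 69.5% for k = 1 at r = 0.3, 0.5, 0.7 and 0.9, and 68.3% for k = 1.25, r = 0.8.

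**3. The regression with its other covariates.** Suppose the listed covariates use q = 10 df and are not prognostic (assumption). The variance of the treatment estimate rises by a factor of about 1 + q/(df − 1). Without baseline, df = 87 and power is 64.3%. With baseline, q = 11 and df = 86. Power is then 74.7%, 70.0% or 65.8% at r = 0.5, 0.7 or 0.9 with k = 1, and 63.9% at k = 1.25, r = 0.8.

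**4. Chance imbalance.** A one-SE baseline difference shifts the change-score estimate by (1 − rk) × s × √(2/n), with n per group. For k = 1, r = 0.5, s = 14:

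- n = 50: 0.5 × 14 × 0.2 = 1.40 points.
- n = 25: 0.5 × 14 × 0.283 = 1.98 points.

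| Case | 50 v 50 | 25 v 25 |
|---|---|---|
| k = 1, r = 0.3 | 1.66 | 2.34 |
| k = 1, r = 0.5 | 1.40 | 1.98 |
| k = 1, r = 0.7 | 1.08 | 1.53 |
| k = 1, r = 0.9 | 0.63 | 0.89 |
| k = 1.1, r = 0.7 | 0.79 | 1.11 |
| k = 1.25, r = 0.7 | 0.39 | 0.55 |
| k = 1.25, r = 0.8 | 0.00 | 0.00 |
| k = 1.25, r = 0.9 | −0.63 | −0.89 |

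In the last row the slope rk exceeds 1, so the change score under-corrects instead.

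**The case against.** The strongest reply is that nothing in the plan is wrong. The change-score contrast is unbiased under randomization, the power table matches the analysis described, and this is a pilot that asks only whether an intervention is promising. All of that stands, and it is why the point concerns precision and not validity.

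It can also be said that the benefit rests on unstated quantities. The 15-point gain needs r = 0.3 with equal SDs, and the gain can be nil. Section 6.5 carries forward an earlier post-baseline value when the 6-month one is missing. The shorter interval may raise the correlation with baseline and, with equal SDs, reduce the gain. The imbalance shift can likewise be zero or change sign. These limits stand too. They make the size uncertain but do not favour leaving baseline out, because the least favourable case shown costs almost nothing.

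The authors did foresee chance baseline differences. Section 5.21n allows baseline measures, quality of life among them, to be used as covariates if relevant. That text belongs to the cancer experience question and does not amend the EQ-5D model in section 6.4.

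Finally, naming a baseline-adjusted model as the main comparison goes further than adding a covariate. It displaces no stated primary test, however, because the plan never says which of its two methods decides.

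**Conclusion.** The concern holds. The EQ-5D regression has a closed covariate list without baseline EQ-5D, and no other section supplies it for that model. Over the cases shown, adding it changes power for 6 points from about 69% to between about 69% and 84%, so the gain runs from nil to about 15 percentage points. With equal SDs and r from 0.3 to 0.7, a one-SE chance imbalance moves a factor estimate by 1.1 to 1.7 points and a pairwise estimate by 1.5 to 2.3 points. With unequal SDs or a high correlation the shift can be much smaller, zero or reversed. The omission is certain, but its size depends on assumed values of r and the SD ratio. The change is worth making, though the planned analysis would not be invalid without it.

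**What to change.** In section 6.4, Second phase:

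- Replace sex with baseline EQ-5D in the covariate list. This carries over to the pairwise contrasts when they are run by regression.
- Name a linear model with the treatment terms plus baseline EQ-5D as the main comparison for each factor. Once baseline is in the model, the treatment estimate is the same whether the outcome is the change or the 6-month score.
- Keep the unadjusted t test and the fuller covariate model as supportive. The other covariates cost degrees of freedom and may not be prognostic.
- Use the baseline score in the same way for anxiety and depression.

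The cost is about two lines of wording, fixed before outcomes are compared by arm. No new data are needed. Statistically it uses one degree of freedom. In the least favourable case shown, calculated power is 68.5% instead of 68.6%.

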### 5.12 Second Phase

A feasibility and acceptability study will employ convenience sampling from 100 consecutive patients who meet inclusion criteria in a pilot randomized trial of:

- Arm 1: Fitbit + active app
- Arm 2: Fitbit + passive app
- Arm 3: Active app
- Arm 4: Passive app

There are two versions of the HOPE smartphone app—“active” and “passive.” The “active” smartphone app refers to the version of the smartphone app in which active symptom collection is occurring (e.g., patients are receiving surveys and receiving tailored symptom management advice) in addition to passive data collection (accelerometer, GPS, Incoming calls and texts, etc.) The “passive” smartphone app refers to the version of the smartphone app in which only passive data collection is occurring, and no surveys or active data collection are being sent to participants. In the passive app, participant interaction with the smartphone app consists of installing the app and keeping it running in the background of their phone; all data is collected in the background. The active and passive apps are built on the same underlying platform and the security protections for the active and passive smartphone apps are identical, detailed in Appendix L, HOPE App Data Privacy and Security.

All patients will be assigned to a separate, secondary randomization either to be encouraged to wear their smartphone on them at all times, or not to be encouraged to wear their smartphone at all times (refer to study schema for details.) We have no reason to believe that encouragement to wear a smartphone will impact patients’ health-related quality of life, performance status, and use of high-intensity health care/phone calls; thus, the secondary randomization will not impact the comparison of the 4 study arms for these outcomes.

With a total sample size of 100 patients (25 patients per arm), this study design will yield 70% power to detect a 6-point change in EQ-5D and 80% power to detect a 7-point change in patients’ health-related quality of life (measured with the EQ-5D; see section 6.0). Our analyses will also provide preliminary estimates of feasibility, acceptability, safety outcomes, scale scores, missing data, and participant and physician feedback.

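### The additional analysis of improvement, no change and decrement uses Fisher's exact test by arm, which ignores order and direction; an ordered test by randomised factor would have about 9 to 10 points more power for a 6-point shift.

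*Combined protocol and SAP*

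**What the plan says.** Section 6.4 (Analysis Plan, Second phase) compares mean EQ-5D change by factor. For the app this sets "all arms that consist of the HOPE app (i.e. arms 1 and 3") against arms 2 and 4, and the Fitbit is handled in the same way. The methods are t tests and linear regression on the continuous change score, supplemented by pairwise comparisons of arms 2, 3 and 4 with arm 1.

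Under additional analyses, the section then plans Fisher's "exact test to compare the proportion of patients in each study arm" with "improvement, no change, or a decrement in quality of life". This is done twice: once for any change from baseline, and once for a 6-point change, which the plan treats as clinically meaningful. It names no trend, rank or proportional-odds analysis of these categories. It gives no error rate or sidedness for the Fisher comparisons, and does not say whether the table is four arms by three categories, pairs of arms, or separate two-way splits.

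Section 6.2 supplies the design figures. For change in EQ-5D, "we will use a one-sided type I error rate of 5" percent; "the standard deviation of the change in EQ-5D at 6 months compared to baseline is approximately 14 points"; "Patients will be randomized 1:1:1:1 to one of the four arms". Section 5.12 states "70% power to detect a 6-point change in EQ-5D and 80% power to detect a 7-point change".

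**The concern.** Decrement, no change and improvement form a scale. Fisher's exact test gives the same p-value however the three columns are arranged, so it cannot use the fact that improvement lies further from decrement than no change does. Two things follow.

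First, if an intervention moves the whole distribution upwards, the test spends part of its sensitivity on patterns that nobody is asking about.

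Second, a small p-value does not mean a shift towards improvement. Suppose 50 controls split 15/20/15 (decrement/no change/improvement) and 50 intervention patients split 21/8/21. Net movement is nil, yet Fisher's p is 0.028, while the exact Wilcoxon test gives p = 1. Section 6.2 sets a one-sided rule for calling an intervention promising on EQ-5D change, and a test without direction cannot follow a rule of that kind.

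The by-arm layout adds to the loss. The categorical comparison, unlike the mean-change comparison, is not set out along the two factors, so it does without the 50 v 50 contrasts on which the trial is powered.

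**Working it through.** **Inputs from the plan.** SD of change 14; 25 per arm, so 50 v 50 per factor; effects of 6 and 7 points; cut at 6 points. **Assumptions.** Change scores are normal, an intervention shifts the mean only, and the control mean change is 0 (varied to -10). The plan gives no control mean and no alpha for this test, so two-sided 5% is assumed.

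**1. Reproduce the plan's power.** SE = 14 × √(2/50) = 2.8. Power = Φ(effect/SE − 1.645), one-sided 5%.
- 6 points: Φ(2.143 − 1.645) = 69.1% (plan: 70%).
- 7 points: Φ(2.500 − 1.645) = 80.4% (plan: 80%).

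The other rows of the section 6.2 table also agree within 2 points.

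**2. Turn the scores into categories.** P(decrement) = Φ((−6 − mean)/14); P(improvement) = 1 − Φ((6 − mean)/14).
- Mean 0: 33.4% / 33.2% / 33.4%.
- Mean 6: 19.6% / 30.4% / 50.0%.

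**3. Power for 50 v 50, by enumerating all 2×3 tables (two-sided 5%, control mean 0).**

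| Shift | Fisher | Exact Wilcoxon | Asymptotic Wilcoxon | Loss (points) |
|---|---|---|---|---|
| 0 | 4.8% | 4.6% | 5.0% | none: type I error |
| 6 | 36.4% | 45.6% | 46.8% | 9.2 to 10.4 |
| 7 | 47.7% | 57.8% | 59.0% | 10.1 to 11.3 |
| 8 | 59.1% | 69.2% | 70.3% | 10.1 to 11.2 |

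With a control mean of −10, a 6-point shift gives 34.6% against 43.4% (exact) or 44.7% (asymptotic), a loss of 8.8 to 10.1 points. Matching to the one-sided 5% rule (Fisher at 10%, one-sided asymptotic Wilcoxon at 5%, control mean 0) gives 49.2% against 59.5%, a loss of 10.3 points.

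**4. Other readings of the planned test.**
- *Four arms by three categories* (4,000 simulated trials, permutation p-values, Fisher v Kruskal-Wallis). App effect 6: 22.9% v 30.7% (7.8 points). App 7: 30.4% v 40.8% (10.3, from unrounded values). App 6 plus Fitbit 3: 28.1% v 38.3% (10.2). App 7 plus Fitbit 3: 36.5% v 47.6% (11.2, from unrounded values).
- *Pairs of arms, 25 v 25.* 6 points: 19.1% v 26.0% asymptotic, 24.1% exact. 7 points: 24.8% v 33.4%, 31.3%. The loss is about 7 to 9 points against the asymptotic test and 5.0 to 6.5 against the exact one.
- *Separate two-way splits, 50 v 50, 6 points.* 32.8% for improvement and 27.7% for decrement, both below the ordered test.
- *Any change, 50 v 50, against the asymptotic test.* The loss is 9.5 to 11.0 points if about 13 to 17% of controls are unchanged, and 7.4 to 8.9 if about 5% are. With nobody unchanged the table is 2×2 and the loss against an equally exact test is zero.

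**5. Where Fisher does better.** Keep the control at mean 0, SD 14, and give the intervention mean 6 with a wider spread (an assumption). At SD 20, Fisher has 31% and exact Wilcoxon 28%.

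**The case against.** The strongest reply is that order is already used where it counts. The primary comparison is directional, by factor and on the continuous score. The categorical comparison is secondary to it, has no power claim to be wrong, and even with an ordered test has less power than the primary analysis. The trial is a pilot intended to establish preliminary effect sizes (section 1.1). This stands, and it keeps the point minor.

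Fisher's test is also valid: type I error is at or below 5% for both tests. A reader might infer from its use that the categorical results would be biased or uninterpretable. The documents do not support that, since the three proportions and the signed mean change would be available beside the p-value.

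Comparing by arm is not in itself a contradiction. Section 6.4 plans pairwise arm comparisons, and several hypotheses in section 2.2 are stated arm against arm. What remains is that no ordered or factor-level test of the categories is named.

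Finally, the ordered test wins only for a shift. If an intervention helps some patients and harms others, the unordered test can be the more sensitive, as step 5 shows. That trade-off is real, but section 6.2 frames the question as a one-sided difference in EQ-5D change, and the descriptive proportions would reveal such a pattern.

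**Conclusion.** The point holds as a minor improvement to an additional analysis. For a location shift in normal change scores (SD 14, 50 v 50, cut at plus or minus 6, two-sided 5%), Fisher gives up roughly 9 to 10 points of power at a 6-point effect. The figure barely moves over assumed control means from 0 to −10. One number does not cover every reading of the plan: the loss is about 8 to 11 points for the four-arm table, up to 7 to 9 for pairs of arms, and from about 11 down to zero for the any-change version.

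A reader might take this as a 10-point loss for the trial. It is not: the stated 70% and 80% belong to the t test on the continuous score, they reproduce, and they are unaffected. Nor do the documents say that the categorical result will lead the report. It deserves a directional test because it is the analysis that applies the 6-point threshold.

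**What to change.** In section 6.4, make an ordered test the stated test for the three-category comparison: exact Wilcoxon or linear-by-linear association, or proportional-odds regression if an effect estimate is wanted. Run it by factor (Fitbit yes/no; active app yes/no), for both the 6-point and the any-change versions. State its sidedness and error rate. Report the three-category proportions in all four arms descriptively, so that any simultaneous rise in improvement and decrement can be seen.

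The cost is a sentence or two in the SAP, with no new data, visits or patients. The one downside is lower sensitivity to a widening of the distribution without a shift.
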